## Research Work Procedure

This research collaborates with the ITB engineering team and the procedure of research is carried out as follows:

1. Selection of subjects according to the criteria of inclusion and exclusion.
2. Research subjects are given an explanation of the research procedure as well as signing informed consent to participate the research.
3. Research subjects who agree to participate in the study sign the informed consent
4. Data registration of the examination form in the medical record
5. Examination of vital signs to see contraindications for further examination. The subjects used a pulse oximetry during the subsequent examination.
6. Upper extremity function assessment is carried out using MMT and FMA UE.
7. Electrical activity recording of deltoid, biceps, triceps, wrist flexors and wrist extensors muscles is performed using sEMG is carried out as follows:
  - a. The subjects are positioned sitting at 60-90 degrees during recording. Put an arm pillow below the impaired hand.
  - b. Preparation of the sEMG (Biograph Infinity) machine for observation the contraction of muscles.
  - c. Clean the skin first using alcohol swab to reduce skin impedance

- d. Ground electrodes are attached to the bone structures in the elbow in the impaired side (olecranon)
- e. Electrodes with diameter 50 mm are placed in impaired side at the anterior deltoid, long head of the biceps, lateral head of the triceps according to the Surface Electromyography for the Noninvasive Assessment of Muscles (SENIAM) guidelines standard placement procedures (Figure 5). Bony anatomical landmarks of the medial and lateral humeral epicondyles were used for standard placement of the subsequent electrodes the wrist flexor and extensor muscle groups, as SENIAM does not offer placement guidelines for these muscles

Figure 5. Electrodes/sensor placement

- f. Each muscle is examined by positioning two electrodes on it, separated by a distance of one or two centimeters
- g. The electrodes are fixed when the electrical activity is clearly visible on the monitor with minimal noise

- h. Muscle signal data were collected for 30 minutes
  - i. During 30 minutes, the subjects do the protocol activity (Figure 6) as describe, for subjects with MMT 0, the researcher then performed a passive range of motion:
    - 00:01:00 (shoulder flexion)
    - 00:02:00 (rest)
    - 00:03:00 (shoulder flexion)
    - 00:04:00 (rest)
    - 00:05:00 (shoulder flexion)
    - 00:06:00 (rest)
    - 00:07:00 (elbow flexion)
    - 00:08:00 (rest)
    - 00:09:00 (elbow flexion)
    - 00:10:00 (rest)
    - 00:11:00 (elbow flexion)
    - 00:12:00 (rest)
    - 00:13:00 (elbow extension)
    - 00:14:00 (rest)
    - 00:15:00 (elbow extension)
    - 00:16:00 (rest)
    - 00:17:00 (elbow extension)
    - 00:18:00 (rest)
    - 00:19:00 (wrist flexion)

- 00:20:00 (rest)
- 00:21:00 (wrist flexion)
- 00:22:00 (rest)
- 00:23:00 (wrist flexion)
- 00:24:00 (rest)
- 00:25:00 (wrist extension)
- 00:26:00 (rest)
- 00:27:00 (wrist extension)
- 00:28:00 rest
- 00:29:00 (wrist extension)
- 00:30:00 (rest)

[figure not shown]

Figure 6. The five movements tested in the experimental setting. Shoulder flexion (a), elbow flexion (b), elbow extension (c), wrist flexion (d), wrist extension (e).

j. The electrodes are released and the scratch area is checked to see if there are any signs of irritation

- k. The subjects are informed that the data collection has been completed, the sEMG engine cleaned up.
8. Surface EMG's signal recording results in digital form were submitted to the ITB Engineering team for the processing of the signal. The results of the electrical activity features of the muscle are contraction, length of contraction and amplitude will be analyzed.
9. All assessment (MMT, FMA UE and sEMG) is carried out at 3 days of stroke onset, the day of discharge from hospital, 1 month, 2 months and 3 months after stroke onset.

[figure not shown]

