## 3. Processing phase

Processing the signal is proses that the raw signal has to be prepared so that it can be easily observed and analysed. The type of processing will depend on the type of analysis we wish to make from the trace.

Many different quantitative parameters can be evaluated from sEMG data such as number of contractions, contraction magnitude, contraction duration, presence of synergistic activations, evaluations of spasticity, or measures of voluntary vs. involuntary contractions.

Surface EMG's signal parameters related to muscle contraction include time analysis and amplitude analysis. The time analysis includes length of contraction. The length of contraction is a parameter for evaluating the period of muscle contraction from manually identified start until end times.

Papazian et al. successfully used the number of contractions, maximum amplitude, median amplitude, and duration from the manually identified start and end times the contractions to measured muscle activity in acute stroke patients. They also evaluated the correlation between the number of contractions, amplitude, and duration. The participants with an MMT of 0, individuals with more contractions had greater maximum amplitude and longer duration contractions.

The primary advantage of sEMG along with its non-invasive nature, is that the signals are relatively straightforward to record and analyse (with some basic signal processing knowledge). It also provides an estimate of the overall activity of a muscle or group of muscles in contrast to the more selective nature of intramuscular recordings.

Surface EMG, however, is only suitable for recording from superficial muscles and is not appropriate for recording deep muscle activity. Recording from small muscles without contamination from surrounding muscles can be difficult and signals can be prone to cross-talk, particularly over regions where there is substantial subcutaneous fat.

Surface EMG's signal has complex nature, and the huge number of variables upon which it depends, so it is important to critically analyse the signal knowing the effects of these variables on its properties. Several years now, an

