increasing number of methodological studies have been undertaken in order to clarify the role of certain experimental factors that can modify signal characteristics, thereby biasing their interpretation. These factors can be classified according to their level of influence on the signal:

1. Technical level: environmental conditions (temperature, humidity, electromagnetic fields) and technical specifications of the equipment (electrodes, electrode-skin interface properties, amplifiers, filters, data acquisition card)
2. Experimental level: measurement procedure (skin preparation, electrode configuration, electrode localisation and orientation) and contraction conditions (ergometer utilised, contraction type, muscle length, contraction level, exercise duration)
3. Descriptive level: signal processing (digitisation, signal characteristics, chosen parameters, used parameter estimates), statistical data analysis (statistical tests)
4. Physiological level: physiological characteristics of the neuromuscular system, either structural (diameter of the active fibres, spatial organisation of fibres in the motor unit and of motor units in the muscle, filtering properties of the tissues, etc) or functional (myotypology, motor unit recruitment, fatigue, muscular coordination, etc.)

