### Premise

Based on the above frame of mind, several premises are compiled as follows:

Premise 1 : Upper extremity weakness is the most common impairment of stroke patients.

Premise 2 : The most significant improvements of upper extremity motor function occur in the first few week post-stroke, often reaching a relative plateau after 3 months with less significant recovery subsequently.

Premise 3 : The presence of any muscle contraction when attempting to perform a movement has positive predictive value on upper extremity prognosis after stroke.

Premise 4 : Muscle contraction is present even among stroke patients characterized as flaccid.

Premise 5 : Surface EMG is useful for the initial evaluation of muscle contraction even for the stroke patients who had an MMT score of zero.

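### Recordings at MMT 0 contain researcher-performed passive motion that other recordings lack; if MMT is applied visit by visit, sEMG change in patients who leave MMT 0 may include a change of recording condition

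*Combined protocol and SAP*

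**What the plan says.** The Research Work Procedure places MMT and FMA-UE testing (step 6) before the sEMG recording (step 7). Step 7h fixes the length: "Muscle signal data were collected for 30 minutes". Step 7i has subjects carry out the listed movements during that time and adds that "for subjects with MMT 0, the researcher then performed a passive range of motion". One timetable follows for everyone, alternating movement and rest, with no entries of its own for passive motion.

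Step 8 sends the signal to the engineering team: "The results of the electrical activity features of the muscle are contraction, length of contraction and amplitude will be analyzed". Step 9 repeats the whole set: "All assessment (MMT, FMA UE and sEMG) is carried out at 3 days of stroke onset, the day of discharge from hospital", and again at one, two and three months.

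The Operational Definition table uses the same wording for every muscle and every recording: activity during contraction, reported as contractions per minute, length and amplitude. Data Analysis and dummy Table 2 compare these parameters between visits within patients, using paired and repeated-measures tests.

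Two of the plan's premises bear on this. Premise 3 reads "The presence of any muscle contraction when attempting to perform a movement has positive predictive value on upper extremity prognosis after stroke". Premise 5 reads "Surface EMG is useful for the initial evaluation of muscle contraction even for the stroke patients who had an MMT score of zero".

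**The concern.** A within-patient comparison needs the same recording conditions at each visit. Here one group of subjects has its limb moved by the researcher during the recording, and entry to that group depends on motor status, which is what is expected to change. A patient who improves from MMT 0 would then differ between visits both in recovery and in what was done while the signal was recorded.

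Table 1 shows how sharp the switch can be. Grade 1 means a trace of contraction without joint motion. A patient moving from 0 to 1 would go from recordings that include a limb moved by the researcher to recordings in which the limb hardly moves. The plan's own literature review names "contraction conditions (ergometer utilised, contraction type, muscle length, contraction level, exercise duration" among the factors that can alter the signal and bias its interpretation.

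The ambiguity falls on the patients for whom premise 5 expects sEMG to be useful, and on the attempted movement that premise 3 relies on.

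**Working it through.** The plan gives no figure on this point to reproduce, and its sample-size calculation does not enter. The check sets the passages side by side.

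**1. The timetable.** Five movements × 3 repeats = 15 movement minutes. With 15 rest minutes this fills the 30. Passive motion therefore has to share the movement or rest minutes, or take the place of the attempts.

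**2. The two readings of 'then' in step 7i.**

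| Reading | Recording at MMT 0 | Recording above MMT 0 |
|---|---|---|
| After the attempt | Attempt plus passive motion | Attempt only |
| Instead of the attempt | Passive motion only | Attempt only |

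The columns differ in both rows, so the difference in condition does not depend on which reading is right.

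**3. Which visit's MMT counts.** Step 7i speaks of subjects with MMT 0, not of visits. MMT comes before sEMG, and step 9 repeats both at five time points, so a per-visit rule is plausible but is an inference.
- Per visit: a patient who leaves MMT 0 changes condition between visits, and the Table 2 comparisons may carry that change.
- Fixed by Day-3 MMT: the condition stays constant within each patient, and only a difference between patients remains.

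**4. Does anything later separate the two?**
- The Operational Definition does not distinguish attempted from passive segments.
- Step 8 describes no label for passive segments.
- The examination form has one MMT entry per visit beside the sEMG entries for five muscles. It identifies MMT 0 visits, but not segments within them. It also does not show whether MMT 0 is judged for the limb or for each movement.
- Data Analysis and Table 2 contain no term or subgroup for recording condition.

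**5. Can the direction be derived?** Let f be the share of movement time that is passive, k the contractions per attempt minute and p the contractions per passive minute. With no recovery at all:
- count with attempts throughout: 15k
- count with passive share f: 15[(1 − f)k + fp]
- relative shortfall: f(1 − p/k)

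The shortfall is zero if f = 0 or p = k, positive if p < k and negative if p > k. The documents give none of f, k or p, so neither sign nor size follows. No comparable expression can be derived for length or amplitude.

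**The case against.** The strongest reply is that step 7i is only loosely worded. It opens by saying that the subjects perform the activity, without exception, and 'then' most naturally means afterwards. That stands. A reader might infer that MMT 0 recordings contain no attempts at all, but the text does not support this as the primary reading. The narrower point survives, because passive motion after an attempt still makes the recording different.

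The per-visit rule is indeed not written down, so the within-patient switch is conditional. The timetable would already locate the passive windows if passive motion replaced the attempt for the whole limb. A marker is missing only where attempted and passive motion share a session or window.

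A reader might also put a figure on the bias by borrowing the cited acute-care study, where 11 of 21 patients had MMT 0. That is another cohort. This plan excludes patients with MoCA-Ina below 26 or GCS below 15, and nothing shows that the share carries over. Nor is the literature review's mention of "measures of voluntary vs. involuntary contractions" a commitment of this plan; it lists what sEMG can measure.

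Finally, the research question is prediction, and visit-to-visit change does not itself test it. This is true, but the comparisons in Table 2 are what the plan proposes to run on the sEMG data.

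Figures 6 and 7 are not available. The Figure 6 caption lists only the five movements, but detail inside the figures could not be checked.

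**Conclusion.** The point holds in a limited form. As written, the plan pools recordings made under unlike conditions, and this is so on either reading of step 7i. That change in sEMG parameters is mixed with a change of condition follows only if MMT status is applied per visit, and only for patients who cross between MMT 0 and a higher grade. If Day-3 MMT governs all visits, what remains is a difference between patients.

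No magnitude is claimed. The effect could be negligible if few patients leave MMT 0 or if passive motion adds and displaces little, and it could run in either direction. A reader might conclude that the sEMG changes in Table 2 will be artefacts, or that a given false-positive rate applies. The documents support neither. Confidence is medium, given the ambiguous wording and the figures that could not be checked. The plan should be changed because the correction is cheap.

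**What to change.** For the procedure:
1. State in step 7i that every subject is cued to attempt each movement at every visit.
2. State whether MMT 0 is judged at each visit, and whether for the limb or for each movement.
3. If passive motion is kept, put it in labelled windows or mark it in the file sent to the engineering team.
4. Compute count, length and amplitude from attempt segments only, use those minutes as the denominator of the per-minute count, and report passive segments separately.

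For recordings already made:
1. Flag MMT 0 visits from the examination form.
2. Repeat the Table 2 sEMG comparisons, as a sensitivity analysis, in patients whose MMT was above 0 at Day 3.
3. State that sEMG change in patients starting at MMT 0 cannot be separated from the change of condition where attempted and passive segments cannot be told apart.

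Cost: the recording stays at 30 minutes. Marking needs at most 15 marks per MMT 0 visit, or 15 × 5 = 75 for a subject at MMT 0 throughout, plus segmentation work for the engineering team. Attempt windows at MMT 0 may fall; for example, if one repeat in three were passive, 5 × 2 = 10 would remain instead of 15. The sensitivity subset is smaller than the full sample and says nothing about MMT 0 patients.

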**Research Flow**

Figure 7. Research flow

## Lampiran 1 Formulir Pemeriksaan

**RUMAH SAKIT UMUM PUSAT [name] SADIKIN BANDUNG**

*[name] SADIKIN GENERAL HOSPITAL BANDUNG*

### FORMULIR PEMERIKSAAN

No. Subjek : .....

Tanggal Pemeriksaan : .....

Tanggal Onset Stroke : .....

Keluahan : .....

#### Data Dasar

Nama	:	Lama tinggal RS	:
No. MR	:	Diagnosa	:
Jenis Kelamin	: L/P	Stroke ulang	: Ya/Tidak
Tanggal lahir	:	Sisi Lesi Otak	:
Usia	:	Sisi Stroke	:
Pendidikan	:	Tangan dominan	:
Faktor Risiko	:		

#### Skrining Kriteria Eksklusi

Gangguan kognitif (MOCA-INA) : .....

Gangguan kesadaran (GCS) : .....

Kondisi medis tidak stabil : .....

Memakai alat pacu jantung : .....

Cedera atau keterbatasan gerak dan kelemahan otot sebelum stroke : .....

Perawatan ruang isolasi : .....

Hipersensitivitas terhadap elektroda gel : .....

#### Pemeriksaan Fisik

Tekanan Darah	:	RR	:
---------------	---	----	---

Nadi	:	Suhu	:
------	---	------	---

SpO2	:	BMI	:
------	---	-----	---

VAS	:	NIHSS score	:
-----	---	-------------	---

## Penilaian dan Pemeriksaan MMT, FMA-UE dan sEMG

No	MMT Score	FMA-UE Score	sEMG				
			Deltoid	Biceps	Triceps	Wrist flexors	Wrist extensors
Pemeriksaan 1			K: LK: A:	K: LK: A:	K: LK: A:	K: LK: A:	K: LK: A:
Pemeriksaan 2			K: LK: A:	K: LK: A:	K: LK: A:	K: LK: A:	K: LK: A:
Follow Up 1			K: LK: A:	K: LK: A:	K: LK: A:	K: LK: A:	K: LK: A:
Follow Up 2			K: LK: A:	K: LK: A:	K: LK: A:	K: LK: A:	K: LK: A:
Follow Up 3			K: LK: A:	K: LK: A:	K: LK: A:	K: LK: A:	K: LK: A:

\*MMT: manual muscle testing, FMA - UE: Fugl Meyer Assessment – Upper Extremity, sEMG : surface electromyography, K: kontraksi, LK: lama kontraksi, A: amplitudo

**Perkiraan jumlah subjek yang akan diikut sertakan:**

30 subjek penelitian

## Lampiran 4. Fugl Meyer Assessment Upper Extremity

**FUGL-MEYER ASSESSMENT**  
**UPPER EXTREMITY (FMA-UE)**  
**Assessment of sensorimotor function**

ID:  
 Date:  
 Examiner:

A. UPPER EXTREMITY , sitting position		
I. Reflex activity	none	can be elicited
Flexors: biceps and finger flexors (at least one)	0	2
Extensors: triceps	0	2
Subtotal I (max 4)		
II. Volitional movement within synergies , without gravitational help	none	partial
Flexor synergy: Hand from contralateral knee to ipsilateral ear. From extensor synergy (shoulder abduction/ internal rotation, elbow extension, forearm pronation) to flexor synergy (shoulder abduction/ external rotation, elbow flexion, forearm supination).	Shoulder retraction elevation abduction (90°) external rotation Elbow flexion Forearm supination	0 1 1 1 0 1 0 1 1 1 0 1 0 1 1 1 0 1 0 1 1 1 0 1
Extensor synergy: Hand from ipsilateral ear to the contralateral knee	Shoulder adduction/internal rotation Elbow extension Forearm pronation	0 1 2 0 1 2 0 1 2
Subtotal II (max 18)		
III. Volitional movement mixing synergies , without compensation	none	partial
Hand to lumbar spine hand on lap	cannot perform or hand in front of ant-sup iliac spine hand behind ant-sup iliac spine (without compensation) hand to lumbar spine (without compensation)	0 1 0 1 0 1
Shoulder flexion 0°- 90° elbow at 0° pronation-supination 0°	immediate abduction or elbow flexion abduction or elbow flexion during movement flexion 90°, no shoulder abduction or elbow flexion	0 1 0 1 0 1
Pronation-supination elbow at 90° shoulder at 0°	no pronation/supination, starting position impossible limited pronation/supination, maintains starting position full pronation/supination, maintains starting position	0 2 0 2 0 2
Subtotal III (max 6)		
IV. Volitional movement with little or no synergy	none	partial
Shoulder abduction 0 - 90° elbow at 0° forearm neutral	immediate supination or elbow flexion supination or elbow flexion during movement abduction 90°, maintains extension and pronation	0 1 0 1 0 1
Shoulder flexion 90° - 180° elbow at 0° pronation-supination 0°	immediate abduction or elbow flexion abduction or elbow flexion during movement flexion 180°, no shoulder abduction or elbow flexion	0 2 0 2 0 2
Pronation/supination elbow at 0° shoulder at 30°- 90° flexion	no pronation/supination, starting position impossible limited pronation/supination, maintains start position full pronation/supination, maintains starting position	0 2 0 2 0 2
Subtotal IV (max 6)		
V. Normal reflex activity assessed only if full score of 6 points is achieved in part IV; compare with the unaffected side	hyper	lively
Biceps, triceps, finger flexors	2 of 3 reflexes markedly hyperactive 1 reflex markedly hyperactive or at least 2 reflexes lively maximum of 1 reflex lively, none hyperactive	0 1 0 1 0 1
Subtotal V (max 2)		
Total A (max 36)		

B. WRIST support may be provided at the elbow to take or hold the starting position, no support at wrist, check the passive range of motion prior testing		none	partial	full
Stability at 15° dorsiflexion elbow at 90°, forearm pronated shoulder at 0°	less than 15° active dorsiflexion dorsiflexion 15°, no resistance tolerated maintains dorsiflexion against resistance	0	1	2
Repeated dorsiflexion / volar flexion elbow at 90°, forearm pronated shoulder at 0°, slight finger flexion	cannot perform volitionally limited active range of motion full active range of motion, smoothly	0	1	2
Stability at 15° dorsiflexion elbow at 0°, forearm pronated slight shoulder flexion/abduction	less than 15° active dorsiflexion dorsiflexion 15°, no resistance tolerated maintains dorsiflexion against resistance	0	1	2
Repeated dorsiflexion / volar flexion elbow at 0°, forearm pronated slight shoulder flexion/abduction	cannot perform volitionally limited active range of motion full active range of motion, smoothly	0	1	2
Circumduction elbow at 90°, forearm pronated shoulder at 0°	cannot perform volitionally jerky movement or incomplete complete and smooth circumduction	0	1	2
Total B (max 10)				

C. HAND support may be provided at the elbow to keep 90° flexion, no support at the wrist, compare with unaffected hand, the objects are interposed, active grasp		none	partial	full
Mass flexion from full active or passive extension		0	1	2
Mass extension from full active or passive flexion		0	1	2
GRASP				
a. Hook grasp flexion in PIP and DIP (digits II-V), extension in MCP II-V	cannot be performed can hold position but weak maintains position against resistance	0	1	2
b. Thumb abduction 1-st CMC, MCP, IP at 0°, scrap of paper between thumb and 2-nd MCP joint	cannot be performed can hold paper but not against tug can hold paper against a tug	0	1	2
c. Pincer grasp, opposition pulpa of the thumb against the pulpa of 2-nd finger, pencil, tug upward	cannot be performed can hold pencil but not against tug can hold pencil against a tug	0	1	2
d. Cylinder grasp cylinder shaped object (small can) tug upward, opposition of thumb and fingers	cannot be performed can hold cylinder but not against tug can hold cylinder against a tug	0	1	2
e. Spherical grasp fingers in abduction/flexion, thumb opposed, tennis ball, tug away	cannot be performed can hold ball but not against tug can hold ball against a tug	0	1	2
Total C (max 14)				

D. COORDINATION/SPEED , sitting, after one trial with both arms, eyes closed, tip of the index finger from knee to nose, 5 times as fast as possible		marked	slight	none
Tremor		0	1	2
Dysmetria	pronounced or unsystematic slight and systematic no dysmetria	0	1	2
		≥ 6s	2 - 5s	< 2s
Time start and end with the hand on the knee	6 or more seconds slower than unaffected side 2-5 seconds slower than unaffected side less than 2 seconds difference	0	1	2
Total D (max 6)				

TOTAL A-D (max 66)	

H. SENSATION , upper extremity eyes closed, compared with the unaffected side		anesthesia	hypoesthesia or dysesthesia	normal
Light touch	upper arm, forearm palmary surface of the hand	0 0	1 1	2 2
		less than 3/4 correct or absence	3/4 correct or considerable difference	correct 100%, little or no difference
Position small alterations in the position	shoulder elbow wrist thumb (IP-joint)	0 0 0 0	1 1 1 1	2 2 2 2
Total H (max12)				

I. PASSIVE JOINT MOTION , upper extremity, sitting position, compare with the unaffected side			J. JOINT PAIN during passive motion, upper extremity			
	only few degrees (less than 10° in shoulder)	decreased	normal	pronounced pain during movement or very marked pain at the end of the movement	some pain	no pain
Shoulder						
Flexion (0° - 180°)	0	1	2	0	1	2
Abduction (0°-90°)	0	1	2	0	1	2
External rotation	0	1	2	0	1	2
Internal rotation	0	1	2	0	1	2
Elbow						
Flexion	0	1	2	0	1	2
Extension	0	1	2	0	1	2
Forearm						
Pronation	0	1	2	0	1	2
Supination	0	1	2	0	1	2
Wrist						
Flexion	0	1	2	0	1	2
Extension	0	1	2	0	1	2
Fingers						
Flexion	0	1	2	0	1	2
Extension	0	1	2	0	1	2
Total (max 24)				Total (max 24)		

A. UPPER EXTREMITY	/36
B. WRIST	/10
C. HAND	/14
D. COORDINATION / SPEED	/ 6
TOTAL A-D (motor function)	/66

H. SENSATION	/12
I. PASSIVE JOINT MOTION	/24
J. JOINT PAIN	/24

